#### 6.1.9. Data Adjustments/Handling/Conventions

All collected data will be presented in listings. Data not subject to analysis according to this plan will not appear in any tables or graphs but will be included in the data listings.

All *P* values will be displayed in three decimals and rounded using standard scientific notation (eg, 0.XXX). If a *P* value less than 0.001 occurs, it will be shown in tables as <0.001.

Adverse events and medical histories will be coded using the Medical Dictionary for Regulatory Activities (MedDRA) version 21.1 thesaurus or higher. Concomitant medications will be coded using WHO Global B3 September 1, 2018.

A treatment-related AE is any AE with a relationship to the study drug of possibly, probably, or definitely related.

If partial AE or medication dates occur, the convention for replacing missing dates for the purpose of statistical analysis is as follows:

For partial AE and medication start dates:

- If the year is unknown, then do not impute the date but assign a missing value.
- If the year is known, but the month or month and day is unknown, then:
  - If the year matches the year of first dose date and the end date (if present) is after first dose date, then impute as the month and day of the first dose date.
  - Otherwise, assign 01 January.

- If the year and month are known, but the day is unknown, then:
  - If the month and year match the month and year of the first dose date, then impute as the day of the first dose date.
  - Otherwise, assign 01.

For partial AE and medication end dates:

- If the year is unknown, then do not impute the date but assign as missing value.
- If the year is known, but the month or month and day is unknown, then:
  - If the year matches the year of the last date of the study (date of last contact if subject lost to follow-up; date of completion or early termination otherwise), then impute as the month and day of the last date of the study.
  - Otherwise, assign 31 December.
- If the year and month are known, but the day is unknown, then:
  - If the month and year match the month and year of the last date of the study, then impute as the day of the last date of the study.
  - Otherwise, assign the last day of the month.

If partial times occur, the convention is as follows:

- if the missing time occurs on the day of the first dose and both the hour and minute are missing then the time assigned is the time of the first dose, otherwise if both the hour and minute are missing and the date is not the date of first dose the time assigned is 12:00;
- if the date is the same as the date of the first dose and
  - only hour is missing the hour assigned is 12 or the hour of first dose, whichever is later;
  - only the minute is missing the minute assigned is 30 or the minute of first dose, whichever is later;
- Otherwise if the date is not the same as the date of first dose, the hour assigned is 12 if the hour is missing and the minute assigned is 30 if the minute is missing.

Partial dates of first ET symptom and partial dates of ET diagnosis will be imputed similar to the rules outlined for AE start dates mentioned above.

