## **2.2. Study Endpoints**

### **2.2.1. Safety Endpoints**

The primary safety endpoint of the study is the occurrence and severity of treatment emergent AEs (TEAEs).

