### **3. Overall Study Design and Plan**

#### **3.1. Overall Design**

This is an open-label study designed to evaluate the safety, tolerability, and efficacy of CAD-1883 administered twice daily orally to adult subjects with ET. The diagnosis of ET must be established by the Principal Investigator at Screening based on the Movement Disorder Society (MDS) criteria with a documented severity of tremor based on the clinician-administered TETRAS-PS.

Commercially Confidential Information

Subjects will undergo a screening period of a minimum of 14 days up to a maximum of 35 days in which the subject will washout from prior Commercially Confidential medications, to allow the effects of previous medication(s) Information CCI to be eliminated. Subjects will return to the site for further assessments on Day 7 (-1 day) and Day 14 ( $\pm 1$  day) and a Follow-up visit (Day 21 [ $\pm 1$  day]). The wearable sensor measurements of upper limb tremor assessments will be completed in the clinic once at any time during the Screening visit and at two different times during the Baseline/Pre-dose site visit.

Commercially Confidential Information

subjects will have the option to complete at-home assessments of tremor using the wearable sensor

Commercially Confidential Information

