#### 6.1.8. Derived Variables

- **TETRAS-PS Total score** = sum of the 16 individual item scores (only the maximum of the item 5 lower limb tremor scores will be counted), with a maximum total score of 64. There will be no missing value imputation performed.
- **TETRAS-PS Upper Limb Subscale score** = sum of the item 4, item 6, item 7 and item 8 scores (forward outstretched postural tremor, lateral “wing beating” postural tremor, kinetic tremor, Archimedes spirals, and dot approximation task from both sides of the body, as well as handwriting), with a maximum total score of 44. There will be no missing value imputation performed.
- **TETRAS-PS Upper Limb Tremor (Item 4) Total score** = sum of the 6 individual scores under item 4 scores (forward outstretched postural tremor, lateral “wing beating”

postural tremor, and kinetic tremor scores for left and right hand, respectively) from both sides of the body, with a maximum total score of 24. There will be no missing value imputation performed.

Commercially Confidential Information

- **Kinesia Upper Limb Tremor score** = sum of the scores from the extended arms posture, wing-beating posture, and kinetic “finger-to-chin” wearable sensor maneuvers from both sides of the body, with a maximum total score of 24. There will be no missing value imputation performed.
- **Change from baseline** = value at current time point – value at baseline.
  - For calculation of change from baseline to Day 14 for discontinued subjects their assessment value at the early termination (ET) visit should be used
- **Percent change from baseline** = (change from baseline / baseline) \* 100. If both baseline and change from baseline are 0 then percent change from baseline will be set to 0.
- **Study day** = number of days relative to the first dose date of study drug and will be calculated using the following formulas:  
For pre-dose: study day= Start Date/ Stop Date – first dose date;  
For post-dose: study day= Start Date/ Stop Date – first dose date + 1.
- **TEAE (treatment-emergent AE)** = any AE with an onset date/time after the first dose of treatment. If an AE was present at baseline and worsened on or after the first dose of treatment it will be considered a TEAE.
- **Orthostatic hypotension** is defined as a reduction in SBP of 20 mmHg or more, and/or a reduction in DBP of 10 mmHg or more, for the standing measurement compared to the supine or semi-supine measurement.

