### **9.1. Adverse Events**

Any AE occurring after the date/time of informed consent signature but prior to the first dose of study medication (ie, occurring during the Screening and Baseline periods) will be listed. All AEs that occur after the first dose of study drug will be considered TEAEs. This includes any AEs that started or worsened (if present at baseline, increased in frequency or severity) after taking the first dose of the study drug. For AEs occurring on the date of first dose, if the time of onset is missing, the AE will be assumed to be treatment emergent.

All AEs will be coded using the MedDRA Version 21.1 or higher coding dictionary.

The causal relationship of the AE to the study drug is determined by the investigator as Not Related, Unlikely Related, Possibly Related, Probably Related, and Definitely Related. These will be mapped to Unrelated (*Not Related or Unlikely Related*) and Related (*Possibly Related, Probably Related, and Definitely Related*).

Adverse events severity grades are reported as mild, moderate, or severe.

Summaries of incidence rates (frequencies and percentages) of individual TEAEs will be presented by SOC, PT, and cohort. Such summaries will be displayed for all TEAEs, TEAEs by maximum severity, and TEAEs by relationship.

Each subject will be counted only once within each summation level (SOC and PT). If a subject experiences more than 1 TEAE within each summation level only the TEAE with the strongest relationship or the maximum severity, as appropriate, will be included in the summaries by subject for relationship and severity, respectively. If a particular event is missing the severity and/or relationship, then the strongest possible severity or relationship will be assumed for analysis (severity=severe, relationship = definitely related).

Incidence will be presented by descending frequency of SOC and PT within SOC, and then alphabetically within PT where the incidence is the same.

Missing and partially missing AE start and/or stop dates will be imputed, for the purpose of statistical analysis, according to the specifications described in Section 6.1.9.

Numbers of AEs will also be presented in these AE summary tables.

In the AE data listings, all AEs will be displayed. AEs that are treatment emergent will be flagged.

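### The SAP does not classify an adverse event whose start year is unknown, and its first-dose-date rules turn some essential tremor diagnosis dates into a one-day history

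*SAP*

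**What the plan says.** **AEs.** The primary endpoint is the occurrence and severity of treatment-emergent AEs (TEAEs) (SAP 2.2.1, Protocol 3.3.1). SAP 6.1.8 defines a TEAE as "any AE with an onset date/time after the first dose of treatment" and adds a second route: "If an AE was present at baseline and worsened on or after the first dose of treatment it will be considered a TEAE".

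SAP 6.1.9 handles incomplete start dates in three branches:
- Year unknown: "If the year is unknown, then do not impute the date but assign a missing value".
- Year known, month unknown: use the month and day of first dose if the year is the first-dose year and any recorded end date is after first dose; otherwise use 1 January.
- Only the day unknown: use the first-dose day if the month is the first-dose month; otherwise use the first of the month.

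SAP 9.1 says "Missing and partially missing AE start and/or stop dates will be imputed", and refers to 6.1.9 for how. An event on the first-dose date with no recorded time is taken as treatment-emergent. For missing severity or relationship, "then the strongest possible severity or relationship will be assumed for analysis".

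**ET history.** SAP 6.1.9 continues: "Partial dates of first ET symptom and partial dates of ET diagnosis will be imputed similar to the rules outlined for AE start dates". Under 6.1.8, time since diagnosis is the Day 1 date minus the diagnosis date, plus 1. SAP 3.1 states: "The diagnosis of ET must be established by the Principal Investigator at Screening". The schedule of events puts Screening 14 to 35 days before Day 1.

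**The concern.** A blank start date cannot be shown to lie after first dose. The only treatment-emergent default in the plan covers a missing time on a known date, not a missing date. A programmer who codes the 6.1.8 definition as written will therefore leave the event out of the TEAE tables. That runs against the rest of the AE handling: missing severity and relationship take the worst case, and an ambiguous date in the first-dose year or month is generally moved onto the first-dose date. Start year is the one incomplete AE field examined here that has no conservative rule, and it feeds the primary endpoint.

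For ET history the difficulty is reversed. Moving an ambiguous date to first dose is cautious for an AE. For a diagnosis that must already exist at Screening, it gives a date that cannot be true.

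**Working it through.** **1. Which AE date patterns are left open.** The 6.1.9 branches were applied with an assumed first dose on 15 July 2019.

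| Recorded start | Recorded end | Date after 6.1.9 | Treatment-emergent by onset? |
|---|---|---|---|
| Year unknown | not used by the rule | missing | cannot be evaluated |
| 2019 only | none | 15 Jul 2019 | yes, with the 9.1 default for missing time |
| 2019 only | 5 Jul 2019 | 1 Jan 2019 | no |
| Jul 2019 | none | 15 Jul 2019 | yes, with the same default |
| Jun 2019 | none | 1 Jun 2019 | no |
| Aug 2019 | none | 1 Aug 2019 | yes |

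Only the first row has no classification.

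**2. Weight of one subject.** If an affected subject has no other TEAE, incidence moves by 100/N percentage points. The SAP (3.2) plans up to 30 subjects: 100/30 = 3.3. Smaller denominators are assumptions: 100/25 = 4.0 and 100/20 = 5.0. Results are also shown by cohort (6.1.2). Cohort sizes are not stated; a cohort of 10, again assumed, gives 100/10 = 10. The documents give no count of such events.

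**3. ET diagnosis.** Keep first dose at 15 July 2019.
- Diagnosis recorded as 2019 only, or as July 2019 without a day: imputed to 15 July 2019. Time since diagnosis = 0 + 1 = 1 day.
- Latest possible diagnosis, at a Screening visit 14 days before Day 1 (1 July): 14 + 1 = 15 days.
- Earliest diagnosis in 2019 (1 January): 195 + 1 = 196 days.

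A true value between 15 and 196 days is thus reported as 1.

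**4. ET first symptom.** Inclusion criterion 2 requires symptoms for at least 3 years before screening, so the first-symptom year cannot be the first-dose year and the faulty branches cannot apply. A year-only date becomes 1 January, which overstates duration by 0 to 364 days. The mean is (0 + 364)/2 = 182 days if onset is uniform over the year. Relative to the mean true duration, for onset years before the first-dose year:
- 5 years: 182/(2022 − 182) = 9.9%
- 10 years: 182/(3848 − 182) = 5.0%
- 20 years: 182/(7501 − 182) = 2.5%

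**5. Would mid-year be safer?** Not by itself. Suppose Screening is on 1 March 2019 and onset is recorded as 2016. An eligible subject's onset was by 1 March 2016, yet 1 July 2016 gives 730 + 243 = 973 days, about 2.66 years. The subject would appear to fail the 3-year criterion.

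**The case against.** The strongest reply is that the SAP nowhere excludes an undated AE; it only leaves the date blank. A reader might infer that such events drop out of the primary endpoint by rule, and the documents do not say so. SAP 9.1 also describes TEAEs by occurrence after first dose. The worsening route in 6.1.8 does not need the original start date. Serious AEs have their own table (14.3.2.2), the overview table has rows for serious AEs and for AEs leading to death, and all AEs are listed. This stands: the event is unclassified, and omission follows only from a literal reading, for new, non-serious events.

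A reader might also see a contradiction between 9.1, which says missing dates are imputed, and 6.1.9, which says not to. That is weak, since 9.1 defers to 6.1.9 and so takes in its exception.

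Rarity stands too. AEs are recorded from consent to Day 21 (Protocol 7.1), participation lasts up to 56 days (Protocol 6.1), and missing data go back to the site as queries (Protocol 12.1.5). An unknown year should nearly always be recoverable.

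On ET history, the SAP asks for rules similar to those for AEs, not identical ones, and the duration is only a baseline descriptor. A reader might infer that ET durations are wrong in general. They are not: the impossible value is confined to the two diagnosis patterns in step 3.

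None of this supplies the missing sentence. The occurrence wording in 9.1 does not help when the timing of the event is exactly what is unknown.

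**Conclusion.** Both gaps are real and small. An AE with an unknown start year has no classification. Coded literally, a new non-serious one is not a TEAE. This can lower the reported incidence but never raise it, and it understates the endpoint whenever the event did start after dosing. The size is 3.3 percentage points per affected subject at 30 subjects, provided that the subject has no other TEAE. Very few such events, quite possibly none, are to be expected.

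For ET diagnosis, dates known only to the first-dose year, or to the first-dose month without the day, yield 1 day where at least about 15 are required. The bound assumes that diagnosis is made no later than a Screening visit 14 days before Day 1. Among the analyses visible in the documents, only a descriptive summary is affected.

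The 1 January convention for other year-only dates is acceptable. Its bias is bounded and in a known direction, and it never makes an eligible subject look ineligible.

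**What to change.** **AEs.** Add to SAP 6.1.9 and 9.1: an AE whose start date remains missing is treatment-emergent unless its end date is before the first dose. This costs one sentence in each section and one programming condition. The downside is that an undated AE from the screening period may be counted as a TEAE, which is in keeping with the SAP's worst-case handling of severity and relationship.

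**ET history.** State that the two first-dose-date branches do not apply to ET history dates, and that no imputed history date may fall after the Screening date. In the example, a 2019-only diagnosis then becomes 1 January (196 days) and a July 2019 diagnosis becomes 1 July (15 days), both possible values. This costs one sentence and a small programming change.

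The 1 January rule for other year-only dates need not change. If a midpoint is preferred, first-symptom dates must also be capped at 3 years before Screening.

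### When only the start day is missing, the AE imputation rule ignores a recorded end date, so an event over before first dose is dated to Day 1 and can be counted as a TEAE

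*SAP*

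**What the plan says.** SAP 6.1.9 treats partial AE start dates in two branches that matter here.

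- **Month (or month and day) missing.** The first-dose month and day are used only under a condition: "If the year matches the year of first dose date and the end date (if present) is after first dose date". If that fails, the instruction is "Otherwise, assign 01 January".
- **Only the day missing.** The instruction is "If the month and year match the month and year of the first dose date, then impute as the day" of first dose. If the month or year differs from first dose, the first of the month is used. The end date plays no part.

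For a start on the first-dose date with no clock time, 6.1.9 adds that if "both the hour and minute are missing then the time assigned is the time of the first dose".

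TEAE status is addressed in more than one place. SAP 6.1.8 defines a TEAE as "any AE with an onset date/time after the first dose of treatment", or an AE present at baseline that worsens once treatment begins. SAP 9.1 opens by saying that "Any AE occurring after the date/time of informed consent signature but prior to the first dose of study medication" is to be listed. It then says of AEs on the first-dose date that "if the time of onset is missing, the AE will be assumed to be treatment emergent". It also brings the 6.1.9 rules into the AE analysis: "Missing and partially missing AE start and/or stop dates will be imputed, for the purpose of statistical analysis". The footnote to Table 14.3.1.1 describes TEAEs as a departure from the subject's baseline condition.

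**The concern.** The two branches treat the same event differently, and the one with more information gives the worse answer on the order of start and end. Where the month is missing, a recorded end before dosing keeps the start before dosing. Where the month is known and matches first dose, the same recorded end is ignored and the start moves to the day of first dose.

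The situation can arise. AEs are collected from consent (Protocol 7.1), and screening lasts 14 to 35 days (SAP 3.1), so an AE can start and finish before dosing within the first-dose month.

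TEAE occurrence and severity is the primary endpoint (SAP 2.2.1 and 9). Presuming treatment emergence is a sensible caution when the order of onset and dosing is unknown. Here the recorded end date settles the order, so counting the event is an error and not a cautious reading.

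**Working it through.** The plan gives no figure to reproduce, so the check is to apply the rules as written. The example dates are assumed. Study days use the SAP 6.1.8 formulas: date minus first-dose date before dosing, and that difference plus 1 from dosing onward.

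**Main example.** Consent in January, first dose 20 February, AE start in February with day and time missing, recorded end 05 February.

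| Item | Date | Study day |
|---|---|---|
| Recorded end | 05 Feb | 5 - 20 = -15 |
| Start, current day-missing rule | 20 Feb | 20 - 20 + 1 = 1 |
| Start, current rule if the month were also missing | 01 Jan | -(30 + 20) = -50 |
| Start, day-missing rule with an end-date check | 01 Feb | 1 - 20 = -19 |

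The current rule puts the start 15 calendar days after the end. With the check, the start (day -19) precedes the end (day -15).

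**TEAE status of that event.** The imputed start is the first-dose date, and the imputed time equals the first-dose time. Under 6.1.8 an onset equal to first dose is not after it, so the event is not a TEAE. Under the missing-time sentence in 9.1, it is. The impossible date arises on either reading; the TEAE count depends on which one is programmed.

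**End on the dosing day.** First dose 20 February 09:00, recorded end 20 February 07:00. The current rules give a start of 20 February 09:00, two hours after the end. A check on dates alone (end not before the first-dose date) would pass this case and change nothing. A check on date and time gives 01 February (day -19).

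**First dose on day 01.** First dose 01 February 09:00, recorded end 01 February 07:00. The first of the month is itself the first-dose date, so the fallback does not help and a separate statement is needed.

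**Generality.** I applied the rule to every first-dose date in an assumed calendar year (2019), for all start and end pairs before the first-dose date, with the start day missing. Every pair whose start month and year matched first dose was dated after its own end: 26,145 of 26,145 for a 14-day window and 56,354 of 56,354 for a 35-day window. With the end-date check, both counts fall to 0. These are calendar counts that show the rule always fails under its conditions. They say nothing about how often such AEs occur.

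**Size.** SAP 9.1 counts each subject once per summation level, so overall incidence moves only if the affected subject has no other TEAE. The step for one such subject is 1/n. With the planned maximum of 30 (SAP 3.2), 1/30 = 3.3 percentage points. Cohort sizes are not given; over an assumed range, 1/20 = 5.0, 1/15 = 6.7 and 1/10 = 10.0 points.

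**The case against.** The strongest reply is that the SAP does not clearly make such an event a TEAE. SAP 6.1.8 requires onset after first dose, the partial-time rule only makes onset equal to it, 9.1 sends pre-dose AEs to a listing, and the table footnote asks for a change from baseline. The one contrary sentence in 9.1 concerns AEs that occur on the first-dose date, and an AE that ended 15 days earlier did not. This is fair, and it limits the claim to *can be counted*. It does not remove the problem: 9.1 also applies the imputed dates to the analysis, no rule gives the recorded end date priority, and the start-after-end date remains.

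The second reply is rarity. The start month and year must match first dose, the end must be recorded and precede dosing, and the start day and onset time must both stay missing. Missing data go to site query (Protocol 12.1.5), inconsistent data must be accounted for (Protocol 12.1.1), and monitors review logical consistency (Protocol 13.4). The AE listing shows start, end and TEAE flag together, so a case would be visible. All of this stands, and the 3.3-point step is simply what any one miscounted subject gives. But imputation rules exist for dates that queries leave unresolved.

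Third, the fallback dates are not accurate either. In the example a 35-day screening window opens on 16 January, so 01 January would normally precede consent; with a shorter screening period 01 February could too. That is true, but both dates keep the event before dosing, which is what TEAE status turns on.

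**Conclusion.** The concern holds. The day-missing rule lacks the end-date check that its neighbour has. Whenever the start month and year match first dose and the recorded end precedes dosing, it gives a start later than the end. If onset time is also missing, following 9.1 literally can place a resolved pre-dose event in the primary endpoint, while 6.1.8 would exclude it.

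The expected effect is small and may be nil. The documents give no rate of missing start days, and the error is toward over-reporting. Each affected subject with no other TEAE moves overall incidence by 3.3 points if 30 are treated, and by more within a cohort. It should be corrected because a stated rule for the primary endpoint yields an impossible result and the correction is nearly free. The same branch covers medication start dates; no claim is made about those.

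**What to change.** In SAP 6.1.9, day-missing branch for AE start dates: impute the first-dose day only if the recorded end is missing or is not before first dose; otherwise assign day 01 of that month. When the end falls on the first-dose date and an end time is recorded, compare date and time. Treat a partial end date that does not settle the order as missing.

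Add two statements, in 6.1.9 and 9.1:

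1. No imputed start date/time may be later than a recorded end date/time.
2. An AE with a recorded end before first dose is not a TEAE, whatever its imputed start.

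Both are needed when first dose falls on day 01, and the second settles the disagreement between 6.1.8 and 9.1 for these events. In the month-missing branch, keep the present strict test or replace it with the same date/time test; do not loosen it to a date-only comparison.

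The cost is a few sentences and a small amount of programming. End date and time are already in Listing 16.2.7. AEs whose order relative to dosing is genuinely unknown keep the cautious default.

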Parameter: Finger-Chin-Finger Quality, Side: Left, Task: Extended Arms Posture,

Parameter: Finger-Chin-Finger Quality, Side: Left, Task: Wing-beating Posture,

Parameter: Finger-Chin-Finger Quality, Side: Left, Task: Kinetic "finger-to-chin" Movement,

Parameter: Finger-Chin-Finger Quality, Side: Left, Task: Arm on Table Posture

Commercially Confidential Information

Commercially Confidential Information

Table 14.3.1.1  
Summary of Adverse Events  
Safety Population

Category	Cohort-1 (N=XX)		Cohort-2 (N=XX)		Overall (N=XX)	
	Subjects n (%)	Events	Subjects n (%)	Events	Subjects n (%)	Events
Subjects with at least 1 TEAE	XX (XX.X%)	XX	XX (XX.X%)	XX	XX (XX.X%)	XX
Maximum Severity of TEAE						
Mild	XX (XX.X%)	XX	XX (XX.X%)	XX	XX (XX.X%)	XX
Moderate	XX (XX.X%)	XX	XX (XX.X%)	XX	XX (XX.X%)	XX
Severe	XX (XX.X%)	XX	XX (XX.X%)	XX	XX (XX.X%)	XX
Subjects with a Related TEAE [1]	XX (XX.X%)	XX	XX (XX.X%)	XX	XX (XX.X%)	XX
Subjects with a TEAE Leading to Discontinuation of Study Drug	XX (XX.X%)	XX	XX (XX.X%)	XX	XX (XX.X%)	XX
Subjects with an AE leading to Death	XX (XX.X%)	XX	XX (XX.X%)	XX	XX (XX.X%)	XX
Subjects with at least 1 SAE	XX (XX.X%)	XX	XX (XX.X%)	XX	XX (XX.X%)	XX
Maximum Severity of SAE						
Mild	XX (XX.X%)	XX	XX (XX.X%)	XX	XX (XX.X%)	XX
Moderate	XX (XX.X%)	XX	XX (XX.X%)	XX	XX (XX.X%)	XX
Severe	XX (XX.X%)	XX	XX (XX.X%)	XX	XX (XX.X%)	XX
Subjects with a Related SAE [1]	XX (XX.X%)	XX	XX (XX.X%)	XX	XX (XX.X%)	XX
Subjects with a SAE Leading to Discontinuation of Study Drug	XX (XX.X%)	XX	XX (XX.X%)	XX	XX (XX.X%)	XX
Subjects with an SAE leading to Death	XX (XX.X%)	XX	XX (XX.X%)	XX	XX (XX.X%)	XX

Abbreviations: TEAE = treatment emergent adverse event; SAE = serious adverse event.

Note: Percentages are n/Number of subjects in the Safety Population and respective Protocol Amendment\*100. AEs were coded using MedDRA version 21.1. A TEAE is any AE that occurs after the time of treatment with the study agent. Events meeting this definition will be those events that are a change from the subject's baseline conditions, including an increase in frequency or severity.

[1] Related TEAEs are those marked as Possibly Related, Probably Related, or Definitely Related on the case report form.

SOURCE: Listing 16.2.7

Table 14.3.1.2  
Incidence of Treatment Emergent Adverse Events by SOC and PT  
Safety Population

System Organ Class Preferred Term	Cohort-1 (N=XX)		Cohort-2 (N=XX)		Overall (N=XX)	
	Subjects n (%)	Events	Subjects n (%)	Events	Subjects n (%)	Events

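### On the first-dose date, the SAP's missing-minute rule can set an AE onset equal to the dose time, which fails the 'after first dose' test for the primary TEAE endpoint

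*SAP*

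**What the plan says.** **Imputation.** For times on the first-dose date, SAP 6.1.9 has three rules:

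- Hour and minute missing: if "both the hour and minute are missing then the time assigned is the time of the first dose".
- Hour missing: if "only hour is missing the hour assigned is 12 or the hour of first dose, whichever is later".
- Minute missing: if "only the minute is missing the minute assigned is 30 or the minute of first dose, whichever is later".

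**Definition.** SAP 6.1.8 defines a TEAE as "any AE with an onset date/time after the first dose of treatment". For an AE already present at baseline the boundary differs: if it "worsened on or after the first dose of treatment it will be considered a TEAE". SAP 9.1 uses *after* for both started and worsened events. The note to Table 14.3.1.1 (SAP 14.2) reads "A TEAE is any AE that occurs after the time of treatment with the study agent", and the notes to Tables 14.3.1.2 to 14.3.1.4 and 14.3.3.1 agree.

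**Default.** For AEs on the first-dose date, SAP 9.1 adds that "if the time of onset is missing, the AE will be assumed to be treatment emergent".

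The occurrence and severity of TEAEs is the primary endpoint (SAP 2.2.1).

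**The concern.** The whichever-is-later wording in SAP 6.1.9 appears meant to stop doubtful Day 1 events from being placed before the dose. It succeeds only as far as a tie, and a tie does not satisfy *after*. A tied event also falls outside the group that SAP 9.1 describes as occurring before the first dose, so it belongs to neither category.

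Whether such an event counts then depends on the minute at which the capsules were taken, which has no clinical meaning. The same tied time would count under SAP 6.1.8 for a worsened condition but not for a new one. Any error is an undercount of events in the hour of first exposure, in a study whose primary endpoint is safety.

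**Working it through.** The plan states no figure to reproduce, so the check applies the SAP 6.1.9 rules and compares each result with the dose time.

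**Inputs.** Rules from SAP 6.1.9; boundary from SAP 6.1.8 and 9.1; up to 30 subjects from SAP 3.2. The documents do not give the clock time of the first dose, so dose hours of 07–11 and 12–14 are assumed. Dose time is H:m.

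| Recorded part of AE time | Imputed time | Against the dose |
|---|---|---|
| Nothing | H:m | Tie, but SAP 9.1 makes it treatment emergent |
| Hour later than H | that hour:max(30, m) | After |
| Hour H, m = 0–29 | H:30 | After |
| Hour H, m = 30–59 | H:m | **Tie** |
| Minute k only, H before 12 | 12:k | After |
| Minute k only, H at 12 or later | H:k | Before if k < m; tie if k = m; after if k > m |

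**Examples, minute missing.** Dose 09:40, AE in hour 09: max(30, 40) = 40, so 09:40, a tie. Dose 09:10, same AE record: max(30, 10) = 30, so 09:30, after.

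**Share that tie, minute missing, dosing hour.** A dose at minute m leaves 59 − m later minutes in that hour.

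- All true post-dose combinations: 59 + 58 + … + 0 = 59 × 60 / 2 = 1,770.
- Combinations with m = 30 to 59: 29 + 28 + … + 0 = 29 × 30 / 2 = 435.
- Share: 435 / 1,770 = 24.6%.

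This assumes evenly spread dose and onset minutes. The number of dose minutes that produce a tie is 30 of 60. That 50% is approached as a share of events only if onsets cluster right after the dose. For example, if every onset comes one minute after the dose and still within the hour, dose minutes 0–58 are possible and 30–58 tie: 29 / 59 = 49%.

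**Hour missing.** With doses at 07–11 h, every imputed time is after the dose. With doses at 12–14 h, the rule keeps the dose hour, so a true onset in a later hour can be moved before the dose. Example: dose 13:40, recorded minute 20, imputed 13:20. Take dose minutes as evenly spread and onsets as evenly spread to midnight. The later hours available for H = 12, 13, 14 are 11 + 10 + 9 = 30.

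- Before the dose: 1,770 × 30 = 53,100.
- Tie: 60 × 30 = 1,800.
- After: 1,770 × 30 + 1,770 × 3 = 58,410.
- Total 113,310, so 46.9% before, 1.6% tie, 51.5% after.

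**Effect of one event.** 1 / 30 = 3.3 percentage points of overall TEAE incidence, if the subject has no other TEAE. In a single cohort column the shift would be larger, because the denominator is smaller; the documents do not give cohort sizes.

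**The case against.** The strongest answer is that SAP 9.1 already settles the matter. It is the AE analysis section, it has a specific rule for the first-dose date, and that rule turns on whether the onset time is missing.

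For fully missing times this stands. A reader might infer from SAP 6.1.9 and 6.1.8 alone that every Day 1 AE with no recorded time becomes a tie and drops out. The documents do not support that: filling in a working value does not change the fact that the time was missing, so SAP 9.1 applies whatever the order of programming.

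For partial times the answer is incomplete. SAP 9.1 does not say whether a time with only the hour or only the minute recorded counts as missing, and SAP 6.1.9 treats these as separate cases with their own rules. Two programmers could reasonably differ.

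A second objection is rarity. The lost record must be a new-onset AE, in the clock hour of a dose given at minute 30 or later, with the hour noted and the minute not. The first dose is taken in the clinic under monitoring (Protocol 6.1.3), vital signs and ECGs follow at 30 and 60 minutes (Protocol 7.8, 7.9), and missing data are queried (Protocol 12.1.5). The event would also still appear in the AE listing. All of this stands and keeps the point minor, but it does not remove the conflict between the two rules.

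**Conclusion.** The point holds in a narrow form. For a new AE on the first-dose date, in the dosing hour, with the minute missing and a dose at minute 30–59, SAP 6.1.9 returns the dose time and the *after* boundary excludes the event unless SAP 9.1 is read to include partial times. With evenly spread minutes this affects about 25% of true post-dose onsets of that kind, rising towards 50% if onsets cluster just after dosing.

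Two stronger readings are tempting and are not supported. One is that partial Day 1 times in general are set to the dose time; most are not, since minute-missing times in later hours and hour-missing times with a dose before noon all fall after the dose. The other is that about half of minute-missing events in the dosing hour are lost; that takes the share of dose minutes for the share of events.

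A missing hour with a dose at or after 12:00 is a related gap, because imputation can land before the dose. It rests on an assumed dosing hour. The number of affected records cannot be derived from the documents and should be small.

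**What to change.** Make two changes together.

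1. In SAP 6.1.8, SAP 9.1 and the notes to Tables 14.3.1.1 to 14.3.1.4 and 14.3.3.1, define a TEAE as an AE with onset or worsening at or after the first dose. Tables that reuse those shells inherit the change.
2. In SAP 9.1, extend the default to partly missing times on the first-dose date: treatment emergent unless the recorded part shows onset before the dose.

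The first change removes ties and the mismatch between new and worsened events. It would not be enough alone, because it does not help an hour-missing time imputed before the dose; the second change does. With both, no true post-dose Day 1 event with a missing or partial time is lost in the cases above.

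The cost is a few words in two sections and five table notes, with no new data. The downside is that an AE that truly began in the minutes before dosing may be counted as treatment emergent. That is the conservative direction for safety, and SAP 9.1 already takes it.
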